3.2 Demographics

Demographics will be collected at screening visits as described in Section 2 and previously collected information will be transferred electronically directly from the parent study's Electronic Data Capture (EDC) system.

3.3 Physical Examination and Weight

A complete physical examination will be performed at the designated study visits as specified in Section 2. Any significant physical examination findings after the first dose will be recorded as adverse events. All findings, whether related to an adverse event (AE) or part of each subject's medical history, will be captured on the appropriate electronic Case Report Form (eCRF) page.

Height will be measured at screening only, if applicable. Body weight will be measured at scheduled visits as part of the physical examination. The subject will wear lightweight clothing and no shoes during weighing.

At any time, a symptom-directed physical examination can be performed as deemed necessary by the Investigator.

3.4 Vital Signs

Vital sign determinations of body temperature, systolic and diastolic blood pressure, pulse rate, and respirations will be obtained at visits as specified in Section 2. Blood pressure and pulse rate should be measured after the subject has been sitting for at least 3 minutes.

3.5 Adverse Event Assessment

Refer to Section 4.2 for details.

3.6 Echocardiogram

An echocardiogram will be performed at the designated study visits as specified in Section 2. The echocardiogram will include assessments of left ventricular ejection fraction and pericardial effusion.

3.7 Dispense Study Drug

Study drug (rovalpituzumab tesirine) will be administered intravenously (IV) to subjects on Day 1 of each treatment cycle, as specified in Section 2. The first dose of study drug will be administered after all other Day 1 procedures are completed. Dexamethasone (or equivalent corticosteroid) will be self-administered twice daily (BID) by subjects on Day –1, Day 1, and Day 2 of each treatment cycle.

Further information on study drug is presented in Section 6.

3.8 Clinical Laboratory Tests

Chemistry

The blood samples for serum chemistry tests should be collected prior to study drug administration. The baseline laboratory test results for clinical assessment for a particular test will be defined as the last measurement prior to the initial dose of study drug.

Local laboratories can be utilized to process and provide results for the clinical laboratory tests, dosing can occur based on results from local laboratories. Laboratory reference ranges will be obtained prior to the initiation of the study. If a laboratory test value is outside the reference range and the investigator considers the laboratory result to be clinically significant, the investigator will:

- repeat the test to verify the out-of-range value;
- follow the out-of-range value to a satisfactory clinical resolution; or

• discontinue the subject from the study or require the subject to receive treatment; in this case, the laboratory result will be recorded as an adverse event.

Clinical Laboratory Tests				
Hematology	Clinical Chemistry	Other Tests		
White blood cell count with five-part differential, to include: Neutrophils Lymphocytes Monocytes Basophils Eosinophils Red Blood Cell (RBC) count Platelet count (estimate not acceptable) Hematocrit Hemoglobin	Sodium Potassium Chloride Carbon dioxide Creatinine Blood Urea Nitrogen (BUN) Estimated glomerular filtration rate Glucose Albumin Total protein Liver function tests, to include: Total and direct bilirubin Alanine transaminase (ALT) Aspartate transaminase (AST) Alkaline phosphatase Lactate dehydrogenase Amylase Lipase	Coagulation tests to include: Prothrombin time (PT) Partial thromboplastin time (PTT) International normalized ratio (INR)		
Color Appearance Specific gravity pH Glucose Bilirubin Ketones Occult blood Protein Spot urine protein Creatinine				

Urinalysis

Dipstick urinalysis will be completed by the central laboratory at all required visits. Specified abnormal macroscopic urinalyses defined as leukocytes, nitrite, protein, ketones, or blood greater than negative, or glucose greater than normal will be followed up with a microscopic analysis at the central laboratory.

Pregnancy Tests (Urine)

A pregnant or breastfeeding female will not be eligible for participation or continuation in this study. Determination of postmenopausal status will be made during the screening period based on the subject's history.

A quantitative urine pregnancy test will be performed on site or by local laboratory as specified in Section 2 for all women of child-bearing potential. If the urine pregnancy test is negative, begin or continue dosing.

Additional testing may be done per the investigator.

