5 STUDY ACTIVITIES

5.1 Eligibility Criteria

Study Entry Criteria

For both Arms A and B; the eligibility criteria are that a subject has enrolled, participated in, and received at least 1 dose of rovalpituzumab tesirine in a parent study.

Arm A Optional Retreatment Criteria

Additional eligibility criterion for Arm A is that subjects who discontinued the study drug in the parent study have completed the treatment emergent AE reporting window (e.g., 30 days post last dose for Study SCRX001-002).

Subjects who elect optional retreatment in Arm A must meet all of the following eligibility criteria before receiving rovalpituzumab tesirine retreatment. Prior to providing retreatment to subjects, study investigators should consult with the AbbVie Medical Monitor.

Demographic and Laboratory Assessments

- 1. Tolerated their initial 2 doses of rovalpituzumab tesirine
- 2. Achieved clinical benefit from rovalpituzumab tesirine, defined as stable disease or better, and is determined that the subject would potentially benefit from additional treatment

Achieved clinical benefit as defined by stable disease or better and experienced radiographic disease progression at least 12 weeks after last dose of rovalpituzumab tesirine per RECIST 1.1

- 3. Received no other systemic anti-cancer therapy after rovalpituzumab tesirine treatment
- 4. Eastern Cooperative Oncology Group (ECOG) performance status of 0 or 1. See the Operations Manual, Appendix B for conversion of performance status using Karnofsky scales, if applicable
- 5. Minimum life expectancy of at least 12 weeks

- 6. Laboratory values meeting the following criteria within the screening period prior to the first dose of study drug:
 - Absolute neutrophil count (ANC) ≥ 1,500/μL;
 - Platelet count ≥ 75,000/μL;
 - Hemoglobin ≥ 8.0 g/dL;
 - Serum total bilirubin $\leq 1.5 \times$ upper limit of normal (ULN) or $\leq 3 \times$ ULN for subjects with Gilbert's disease;
 - Serum alanine aminotransferase (ALT) and aspartate aminotransferase (AST) ≤ 2.5 × ULN (≤ 5 × ULN if evidence of hepatic involvement by malignant disease);
 - Serum creatinine ≤ 1.5 × ULN or estimated glomerular filtration rate (eGFR)
 ≥ 30 mL/min/1.73 m² as calculated by the 4-variable Modification of Diet in Renal Disease study equation (GFR (mL/min/1.73 m²) = 175 × (serum creatinine [mg/dL])-1.154 × (age [years])-0.203 × 0.742 (if female) × 1.212 (if African American).³

Disease Activity

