5.6 Follow-Up for Subject Withdrawal from Study

To minimize missing data for efficacy and safety assessments, subjects who prematurely discontinue study drug treatment should continue to be followed for all regularly scheduled visits, unless subjects have decided to discontinue the study participation entirely (withdrawal of informed consent). Subjects should be advised on the continued scientific importance of their data even if they discontinue treatment with study drug early.

If a subject prematurely discontinues study participation (withdrawal of informed consent), the procedures outlined for the Premature Termination Follow Up (PTFU visit) should be completed as soon as possible, preferably within 2 weeks. All attempts must be made to determine the date of the last study drug dose and the primary reason for discontinuation of study drug or study participation. The information will be recorded on the appropriate electronic Case Report Form (eCRF) page. However, these procedures should not interfere with the initiation of any new treatments or therapeutic modalities that the Investigator feels are necessary to treat the subject's condition. Following discontinuation of study drug, the subject will be treated in accordance with the Investigator's best clinical judgment, irrespective of whether or not the subject decides to continue participation in the study.

Subjects no longer undergoing clinical assessments will have survival information collected approximately every 6 weeks until the endpoint of death, the subject becomes lost to follow-up or withdraws consent, or termination of the study by AbbVie, whichever occurs first. In addition, if the subject is willing, a 70-day follow-up phone call after the last dose of study drug may be completed to ensure all treatment-emergent AEs/SAEs have been resolved.

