Certain AEs are anticipated to occur in this study population at some frequency independent of drug exposure. Such events include known consequences of the underlying disease or condition under investigation (e.g., symptoms, disease progression). These AEs may occur alone or in various combinations and are considered expected AEs in subjects and for reporting purposes for this protocol. "Disease progression" should not be captured when reporting AEs or SAEs, even if fatal, as disease progression will be captured as efficacy outcomes in the trial. Rather, symptoms of disease progression should be reported as AEs or SAEs and the distinction on the AE eCRF marked as appropriate.

Deaths Due to Cancer Progression

For SAEs with the outcome of death, the date and cause of death will be recorded on the appropriate eCRF. Further details are provided in the Operations Manual, Section 4.1.

Pregnancy

Pregnancy in a study subject must be reported to AbbVie within 1 working day of the site becoming aware of the pregnancy. Subjects who become pregnant during the study must discontinue study drug.

All subjects should be informed that contraceptive measures (refer to Section 5.2) should be taken throughout the study and for at least 6 months after the last dose of study drug. Male subjects should be informed that contraceptive measures should be taken by their female partner.

Information regarding a pregnancy occurrence in a study subject and the outcome of the pregnancy will be collected. In the event of a pregnancy occurring in the partner of an enrolled subject, written informed consent for release of medical information from the partner must be obtained prior to the collection of any pregnancy specific information, and the pregnancy will be followed to outcome.

Pregnancy in a study subject is not considered an AE. The medical outcome for either mother or infant, meeting any serious criteria including an elective or spontaneous abortion, is considered a SAE and must be reported to AbbVie within 24 hours of the site becoming aware of the event.

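### Operations Manual 3.8 bars pregnant or breastfeeding women from the study rather than from study drug, contrary to Protocol 6.1 with 5.6 (staying in, pregnancy only) and 5.1 (entry to Arm A follow-up)

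*Combined protocol and SAP*

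**What the plan says.** Operations Manual 3.8, under the pregnancy test heading, states: "A pregnant or breastfeeding female will not be eligible for participation or continuation in this study". The paragraph after it ties the test result to treatment: "If the urine pregnancy test is negative, begin or continue dosing".

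The protocol treats the same situation in three places:

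- Section 6.1 (Pregnancy): "Subjects who become pregnant during the study must discontinue study drug". It adds: "Information regarding a pregnancy occurrence in a study subject and the outcome of the pregnancy will be collected".
- Section 5.6: "subjects who prematurely discontinue study drug treatment should continue to be followed for all regularly scheduled visits". The one exception is a subject who withdraws consent altogether.
- Section 5.1: for both arms "the eligibility criteria are that a subject has enrolled, participated in, and received at least 1 dose of rovalpituzumab tesirine", meaning in a parent study. Arm A adds only that subjects who stopped drug in the parent study have completed its adverse event reporting window. The pregnancy and breastfeeding items come later, in a numbered list that subjects choosing Arm A retreatment "must meet all of the following eligibility criteria before receiving rovalpituzumab tesirine retreatment".

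Protocol 8.2 requires the study to be run according to both the protocol and the Operations Manual.

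**The concern.** Protocol 3.1 gives long-term follow-up of subjects whose parent studies are closing as the objective. A woman who has already received rovalpituzumab tesirine is the kind of person the study exists to follow, whether or not she can be dosed again. Taken literally, 3.8 would remove a treated subject who becomes pregnant. It would also refuse a pregnant or breastfeeding woman who wants only Arm A follow-up, and with her parent study closing she would then have no follow-up here. A site cannot comply with 3.8 and with the protocol sections above at the same time, and Protocol 5.9 prohibits deviations except to remove an immediate hazard.

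**Working it through.** No arithmetic applies. The documents give no pregnancy rate and Protocol 7.6 sets no sample size. The check is to set the rules side by side.

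**1. Scope of the sentence.** It covers both entering the study and staying in it, and it names the study, not drug or dosing. The protocol keeps those two levels apart: 5.6 handles stopping drug and leaving the study in separate paragraphs, and 7.3 lists the two kinds of discontinuation separately. The study-level words in 3.8 therefore have a distinct meaning.

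**2. Staying in (pregnancy only).** Take a subject dosed in this study who becomes pregnant.

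- Under 3.8 she leaves the study.
- Under 6.1 she stops drug and the pregnancy is followed to its outcome. No study exit is called for.
- Under 5.6, having stopped drug early, she stays on the scheduled visits.
- Under Operations Manual 2.3, survival follow-up ends with death, loss to follow-up, withdrawal of consent or termination by the sponsor. Pregnancy is not on that list.

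The first rule contradicts the other three. Section 6.1 does not mention breastfeeding, so this part of the conflict concerns pregnancy alone.

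**3. Entry, by route.**

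| Route | Study drug in this study | Pregnancy or breastfeeding criterion in Protocol 5.1 | Pregnancy test scheduled | Reading of 3.8 |
|---|---|---|---|---|
| Arm A, follow-up only | No; visits may all be by phone (Operations Manual 2.1) | None | No (2.1) | Adds an exclusion that 5.1 lacks, with no dosing reason |
| Arm A, retreatment | Yes | Items 9 to 13; breastfeeding in item 10 | Yes (2.2) | Agrees as far as dosing goes |
| Arm B | Yes | None | Yes (2.3) | 5.1 is silent; a bar on dosing is appropriate |

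The clear entry conflict is in the first row, and there it covers both pregnancy and breastfeeding.

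**4. What data could be affected.** For treated subjects, Protocol 3.3 and Operations Manual 4.1 require all adverse events through 70 days after the last dose, and drug-related serious events after that. Neither makes an exception for early exit. For Arm A subjects without treatment, drug-related serious events are collected. Survival contacts (5.6) and pregnancy outcome (6.1) have their own rules for enrolled subjects. Protocol 7.4 and 7.5 plan only listings and a descriptive safety summary for disclosure, so no formal analysis is involved.

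**The case against.** The strongest reply is that context makes the meaning plain. The sentence sits in a laboratory section under the pregnancy test heading, and the next paragraph speaks of dosing. Tests are scheduled only where drug is given, and Operations Manual 2.2 refers the reader to Protocol 5.1 for the retreatment criteria. On that reading no site would apply the rule to a woman followed by phone who is never tested. This is good evidence of what was intended, and it is a reason to expect few cases. It does not narrow a sentence that names participation and continuation in the study.

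A second reply is that the withdrawal reasons in Protocol 5.5 are open-ended. That stands, but it allows the investigator to withdraw an individual in her interest. It does not make exit automatic, as 3.8 does.

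Other objections limit how far the point can go. A reader might infer any of the following, and the documents do not support them:

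- *A measurable loss of adverse event reporting.* Section 5.6 says that "a 70-day follow-up phone call after the last dose of study drug may be completed", so the call is optional, and one could count the days lost after an early exit. The count would rest on an assumed exit date and on the site setting aside the day-70 requirement in 3.3 and Operations Manual 4.1.
- *A problem with the analysis set.* Protocol 7.2 requires all eligibility criteria to be met, but this bites only if a laboratory paragraph counts as an eligibility criterion, and 7.2 allows for other specification.
- *An equal conflict for Arm B entry.* Section 5.1 says nothing about pregnancy for Arm B, and keeping a pregnant woman from dosing there is sensible.
- *That no rule says which document prevails.* I found none in the text available, but parts of the appendices were not included, so I do not claim there is none.

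**Conclusion.** The point holds in a limited form and is minor. Operations Manual 3.8 contains a wrong rule, not merely a missing detail. It conflicts with Protocol 6.1 read with 5.6 on whether a subject who becomes pregnant stays in the study. It also adds a pregnancy and breastfeeding exclusion to Arm A follow-up that 5.1 does not contain. Excluding these women from drug in Arm B or Arm A retreatment is not in question.

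The number of subjects affected cannot be derived from the documents; that it is small is my assumption. No figure for lost adverse event data should be attached. At most, some listings and the descriptive safety summary would be incomplete, and only if a site followed 3.8 in preference to the protocol. Confidence is high for the conflict in wording and low for any practical effect.

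**What to change.** Replace the sentence in Operations Manual 3.8 with:

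> A pregnant or breastfeeding female is not eligible to receive or continue study drug (Arm A retreatment or Arm B). She may enter or remain in follow-up without study drug; AE/SAE reporting continues per Protocol 3.3 and Operations Manual 4.1, scheduled visits and survival follow-up per Protocol 5.6 and Operations Manual Section 2, and pregnancy reporting per Protocol 6.1.

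The rest of 3.8, the drug-stopping rule in 6.1 and the withdrawal reasons in 5.5 stay as they are. A woman who would have entered on ongoing treatment would stop drug, and would then fit Arm A once her parent-study reporting window has closed (5.1).

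The change needs no new visits, tests or staff, because existing schedules apply. Protocol 8.1 requires ethics committee approval of an amendment, so it can go in with the next one.

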3.9 Other Assessments

All assessments take place as described in Section 2.

Eastern Cooperative Oncology Group (ECOG) scale will be used to assess performance status at the Screening visits in Arm A retreatment and Arm B. For conversion of performance status using Karnofsky scales to ECOG, see Appendix B.

MRI of the brain (if clinically indicated) should be performed to confirm absence of active central nervous system (CNS) tumor or metastases. Brain MRI may be substituted by computerized tomography (CT) with IV contrast at the discretion of the investigator if MRI testing is clinically contraindicated, not available, or if the subject is unable to tolerate MRI. MRI assessments will be performed at study visits as specified in Section 2.

CT imaging of the chest, abdomen, and pelvis, and neck (if indicated) as well as other relevant imaging, as described via RECIST v1.1, will be used for disease/response assessment. Assessment of response and progression will be determined by the investigator according to RECIST v1.1. These assessments will be conducted at study visits as specified in Section 2. Upon disease progression or initiation of new anticancer therapy, disease/response assessment will consist of subsequent anticancer therapies and dates, date of progression (if not already captured), and survival status. No subsequent radiography is required once disease progression has occurred.

Ongoing concomitant therapies (from subject's parent study) should be recorded at study visits as specified in Section 2 and will include the names of all concomitant medications, blood products, procedures, and radiotherapy, including dates of administration, dose regimen, route of administration, and purpose.

Subjects enrolled in Arm B or Arm A Retreatment will complete fluid retention questionnaires starting on Day 1 through the EOT Visit (refer to Section 2). Subjects will record their daily weights or new edema or dyspnea on the fluid retention questionnaire (Appendix C). Fluid retention questionnaires will be distributed to subjects on Day 1, Day 15, Day 29, and the Post-Cycle Response Assessment Visit. Each questionnaire records up to 7 days of daily weights and subjects should be provided with enough questionnaires to record their daily weight until their next on-site clinic visit.

Sites will call subjects between on-site clinic visits to review completed fluid retention questionnaires. The fluid retention questionnaire follow-up phone calls will be performed at Day 7 + 2 Days,

Day 22 + 2 Days, and Day 36 + 2 Days. Subjects should be instructed to use a consistent weighing device throughout the study.

4 SAFETY MANUAL

4.1 Methods and Timing of Safety Assessment

Adverse Event Reporting in Arm A and B Subjects who Receive Treatment or Retreatment in This Study

Within the 70 Day Follow-Up Period

Treatment-emergent adverse events (TEAEs) and treatment emergent serious adverse events (SAEs) will be collected; TEAEs and treatment emergent SAEs are defined as those that occur or worsen on or after the first dose of study drug until 70 days after the last dose of study drug.

After the 70 Day Follow-Up Period

All SAEs that occur after the safety reporting period that are considered study drug-related in the opinion of the Investigator should also be reported.

Adverse Event Reporting in Arm A subjects who do not Receive Treatment or Retreatment in This Study

All SAEs that are considered study drug-related in the opinion of the Investigator should be reported.

Deaths due to Cancer Progression

[figure not shown]
Deaths that occur during the protocol specified AE/SAE reporting period (Section 2) that are more likely related to disease progression will therefore be considered as an expected AE and will not be subject to expedited reporting. After the AE reporting period, deaths attributed to progression of disease under study should not be recorded on the AE eCRF, but on the Survival Death eCRF.

Death should be considered an outcome and not a distinct event. The event or condition that caused or contributed to the fatal outcome should be recorded as the single medical concept on the AE eCRF. Generally, only 1 such event should be reported. The term "sudden death" should only be used for the occurrence of an abrupt and unexpected death due to presumed cardiac causes in a subject with or without pre-existing heart disease, within 1 hour of the onset of acute symptoms or, in the case of an unwitnessed death, within 24 hours after the subject was last seen alive and stable. If the cause of death is unknown and cannot be ascertained at the time of reporting, "unexplained death" should be recorded on the AE eCRF. If the cause of death later becomes available (e.g., after autopsy), "unexplained death" should be replaced by the established cause of death.

The survival status of subjects will be ascertained according to a predetermined follow-up schedule (Section 2). The follow-up schedule is intended to provide for the systematic ascertainment of each subject's survival status (alive, dead, or unknown/lost to follow-up) until the closure of the extension study. For subjects lost to follow-up or whose survival status is unknown, every effort will be made to determine the date such subjects were last known to be alive. Such efforts may include phone calls, certified mail, and the checking of public records.

Information will be collected as the diagram below.

